4.3 JUSTIFICATION FOR DOSE

The recommended clinical starting dose (50 mg) in advanced cancer patients is based on the 28-day repeat-dose toxicity study in dogs, with the highest non-severely toxic dose (HNSTD) at 10 mg/kg/day. Taking one-sixth the HNSTD dose as outlined in ICH S9, then correcting for body surface area, equates to a recommended starting dose of 0.93 mg/kg, or 55.6 mg for a 60 kg patient. Therefore, a 50 mg starting dose was suggested as the safe starting dose for the Phase 1 Monotherapy Dose Escalation study.

In the ZN-c5 food effect Study ZN-c5-006, the ratio of AUC_{0-inf} after a high-fat meal compared to fasting showed no effect. A small, <20%, decrease in C_{max} was observed when ZN-c5 was administered after a high-fat meal. Although the C_{max} change was statistically significant (lower 90% confidence bound < 0.8), the difference was small compared to the variability of the ZN-c5 exposure in cancer patients and therefore not considered clinically relevant. Based on these results (data on file), ZN-c5 is allowed to be dosed with or without food. This will be implemented only in the Phase 2 parts of the protocol.

4.4 END OF STUDY DEFINITION

The end of the study is defined as when the last patient on study has completed their last study visit (i.e., last safety follow-up or last disease assessment follow-up, whichever is last).

If the primary objectives of the study have been met or the Sponsor decides to stop the study early, the database may be locked for the purpose of analyzing and reporting data. Subjects may continue to receive ZN-c5 per protocol beyond the data cut-off for database lock if the Investigator and the Sponsor agree that the patient's best interests are served by remaining on study treatment.

Limited information including, but not limited to study drug administration, study drug accountability, and non-serious and serious adverse events will be collected in addition to any cases of pregnancy, overdose, or medication error. Less frequent subject visits might be implemented as per institutional standard of care.

5 STUDY POPULATION

5.1 INCLUSION CRITERIA

Subjects must meet all of the following inclusion criteria to be eligible for participation in this study:

- 1) Male or female
- 2) Age ≥ 18 years
- 3) Menopausal Status [Female subjects]:

Postmenopausal, as defined by at least one of the following

- a) Age \geq 60 years;
- Age < 60 years and cessation of regular menses for at least 12 consecutive months with no alternative pathological or physiological cause; and serum estradiol and FSH level within the laboratory's reference range for postmenopausal females;
- c) Documented bilateral oophorectomy;

or

Pre- or peri-menopausal, who must receive a gonadotropin-releasing hormone agonist beginning at least 4 weeks prior to first dose of study medication.

- 4) Histologically or cytologically confirmed diagnosis of advanced adenocarcinoma of the breast, not amenable to any potential curative intervention
- 5) Estrogen Receptor (ER) positive disease defined as follows documented by a local laboratory:
 - a) [Monotherapy Escalation and Combination Dose Escalation Cohorts]: > 1% positive stained cells based on medical record, archival tumor biopsy, or *de novo* tumor biopsy
 - b) [Monotherapy Expansion/Monotherapy Phase 2/Combination Phase 2 Cohorts]: > 10% positive stained cells
- 6) Human Epidermal Growth Factor Receptor 2 (HER2) negative disease as documented by a local laboratory
 - a) [Monotherapy Escalation and Combination Dose Escalation Cohorts]: Documentation by medical record or archival tumor tissue allowed
 - b) [Monotherapy Expansion/Monotherapy Phase 2/Combination Phase 2 Cohorts]: Based on analysis of archival tumor biopsy or *de novo* biopsy with HER2-negativity defined as: 1) Immunohistochemistry score 0/1+ or 2) Negative by *in situ* hybridization (FISH/CISH/SISH) defined as a HER2/CEP17 ratio < 2, or for single probe assessment a HER2 copy number < 4

- 7) [Monotherapy Escalation and Combination Dose Escalation Cohorts]: Refractory to or intolerant of established therapy(ies) known to provide clinical benefit for their malignancy
- 8) Prior Hormonal Therapy:
 - a) [Monotherapy Expansion Cohort]: up to 2 prior lines of endocrine therapy for advanced or metastatic breast cancer
 - b) [Monotherapy Phase 2]: 1 or 2 prior lines of endocrine therapy for advanced or metastatic breast cancer
 - c) [Combination Phase 2]: up to 1 prior line of endocrine therapy for advanced or metastatic breast cancer

- d) Subjects who will undergo a FES-PET must have discontinued all prior ER blocking therapy (e.g., tamoxifen or fulvestrant) for ≥ 60 days before the day of the examination at baseline.
- In counting lines of treatment for advanced/metastatic disease, any change in regimen due to PD or toxicity will be counted as a separate line of treatment.
- 9) Documented prior response to endocrine therapy for advanced or metastatic disease (SD, PR, or CR) lasting > 6 months or disease recurrence after at least 24 months of adjuvant endocrine treatment. (not required for treatment naïve patients)
- 10) Prior Chemotherapy:
 - a) [Monotherapy Dose Escalation Cohort]: Up to 2 prior lines of chemotherapy for the treatment of advanced breast cancer
 - b) [Monotherapy Phase 2]: No prior chemotherapeutic regimens for the treatment of advanced breast cancer
 - c) [Monotherapy Expansion, Combination Dose Escalation and Combination Phase 2 Cohorts]: Up to 1 prior line of chemotherapy for the treatment of advanced breast cancer

In counting lines of treatment for advanced/metastatic disease, any change in regimen due to PD or toxicity will be counted as a separate line of treatment.

- 11) Prior treatment with a CDK4/6 inhibitor is allowed
- 12) Evaluable or measurable disease per RECIST v1.1.
- 13) Eastern Cooperative Oncology Group (ECOG) Performance Status of ≤ 2
- 14) All acute toxic effects of any prior anti-tumor therapy resolved to Grade ≤ 1 or baseline (with the exception of alopecia [any grade permitted])
- 15) Adequate organ function defined as follows:
 - a) Hematologic: Platelets $\geq 100 \times 10^9$ /L; Hemoglobin ≥ 9.0 g/dL; Absolute Neutrophil Count (ANC) $\geq 1.5 \times 10^9$ /L (without platelet transfusion or any growth factors within previous 7 days of the hematologic laboratory values obtained at Screening visit).
 - b) Hepatic: Aspartate transaminase (AST) and Alanine transaminase (ALT) ≤ 2.5 × upper limit of normal (ULN) or ≤ 5 × ULN in case of liver metastases; Total or conjugated bilirubin ≤ 1.5 × ULN.
 - c) Renal: Creatinine clearance (CrCl) ≥ 30 mL/min as calculated by the Cockcroft Gault method or serum creatinine ≤ 1.5 × ULN
- 16) [Premenopausal and perimenopausal female subjects]: Negative serum pregnancy test
- 17) Male and female subjects of childbearing potential or partners of subjects who engage in intercourse must agree to use protocol specified method(s) of contraception.

5.2 EXCLUSION CRITERIA

Subjects who meet any of the following exclusion criteria are not to be enrolled in this study:

- 1) Any of the following within the specified window prior to the first dose of study drug:
 - a) Tamoxifen, AI, fulvestrant or other anti-cancer endocrine therapy < 14 days
 - b) Any chemotherapy < 28 days (or 5 half-lives, whichever is shorter)
 - c) Any investigational drug therapy < 28 days or 5 half-lives (whichever is shorter)

- d) Prior radiotherapy < 14 days (except for palliative radiotherapy to peripheral sites without residual toxicity)
- e) Major surgery < 28 days
- f) Minor surgery < 7 days (placement of central venous catheter, fine needle aspiration, or endoscopic biliary stent < 1 day is acceptable)
- 2) Prior hematopoietic stem cell or bone marrow transplantation
- 3) Prior radiotherapy to > 25% of bone marrow
- 4) Brain metastases that require immediate treatment or are clinically or radiologically unstable (i.e., have been stable for < 1 month). If receiving steroids, subjects must be receiving a stable to decreasing corticosteroid dose during at least 1 week before enrollment.
- 5) Leptomeningeal disease that requires or is anticipated to require immediate treatment.
- 6) Presence of life-threatening metastatic visceral disease or symptomatic pulmonary lymphangitic spread
- 7) Other known active cancer(s) likely to require treatment in the next year that would impact the assessment of any study endpoints
- 8) [Female subjects]: Pregnant or breast-feeding
- 9) Unexplained symptomatic endometrial disorders (including, but not limited to endometrial hyperplasia, dysfunctional uterine bleeding, or cysts)
- 10) Uncontrolled symptomatic thyroid dysfunction
- 11) Impairment of gastrointestinal (GI) absorption for oral medications
- 12) Nausea, vomiting, or diarrhea > Grade 1
- 13) Myocardial infarction, symptomatic congestive heart failure (NYHA > Class II), unstable angina, or serious uncontrolled cardiac arrhythmia within the last 6 months
- 14) QTc interval > 480 msec (based on the mean value of the triplicate ECGs), family or personal history of long or short QT syndrome, Brugada syndrome or history of Torsade de Pointes
- 15) Concurrent use of food or drugs known to be moderate or strong CYP3A or CYP2C9 inducers and moderate or strong CYP3A4 or CYP2C9 inhibitors. In addition, for moderate or strong CYP3A or CYP2C9 inducers, there should be a wash-out of 14 days (or 5 half-lives, whichever is shorter) before the first administration of study drug (see Section 10.4.6).
- 16) Any clinically significant disorder, condition, or disease that, in the opinion of the Investigator or Medical Monitor would pose a risk to subject safety or interfere with the study evaluations, procedures, or completion

5.3 LIFESTYLE CONSIDERATIONS

Not applicable.

5.4 SCREEN FAILURES

Screen failures are defined as participants who consent to participate in the clinical trial but are not subsequently entered on study. A minimal set of information will be collected from these participants to ensure transparent reporting of screen failure participants, to meet the Consolidated Standards of Reporting Trials (CONSORT) publishing requirements and to respond to queries from regulatory

authorities. The information collected will include demography, screen failure details, and eligibility criteria. Subjects may be rescreened after discussion with the Sponsor.

5.5 STRATEGIES FOR RECRUITMENT AND RETENTION

Not applicable.

STUDY INTERVENTION

6.1 STUDY INTERVENTION(S) ADMINISTRATION

6.1.1 STUDY INTERVENTION DESCRIPTION

6.1.1.1 ZN-c5

ZN-c5 is an oral selective estrogen degrader (SERD) that binds potently to the estrogen receptors alpha and beta (ER α and ER β). ZN-c5 has not been tested in humans prior to this study. See Investigator's Brochure (IB) for details of ZN-c5.

6.1.1.2 PALBOCICLIB

Palbociclib (IBRANCE®, Pfizer Inc.) is an orally active pyridopyrimidine that is a potent and highly selective reversible inhibitor of Cyclin-Dependent Kinases 4 and 6 (CDK 4/6). The compound prevents cellular DNA synthesis by prohibiting progression of the cell cycle from G1 into the S phase, as demonstrated both in laboratory models and in early clinical trials. There is a strong link between the action of estradiol on the G1-S phase transition, where it drives transcriptional activation of cyclin D1 leading to formation of the cyclin D1-CDK4/6-Rb complex which facilitates the G1 to S phase transition. In nonclinical experiments, palbociclib synergizes with antiestrogen to cause tumor regression in in vitro ER+ advanced breast cancer cell lines. Based on the results of the PALOMA-2 study, palbociclib is approved by the US FDA and other Health Authorities for the treatment of for the treatment of HR+, HER2-negative advanced or metastatic breast cancer in combination with an AI as initial endocrine based therapy in postmenopausal women. Additionally, based on the results of the PALOMA-3 trial which showed a statistically significant improvement in PFS (9.5 months vs 4.6 months for placebo + fulvestrant), palbociclib is approved for the treatment of HR-positive, HER2-negative advanced or metastatic breast cancer in combination with fulvestrant in women with disease progression following endocrine therapy.

6.1.2 DOSING AND ADMINISTRATION

6.1.2.1 DOSING AND ADMINISTRATION OF ZN-c5

ZN-c5 capsules (25 and 100 mg) will be provided by Zeno Alpha.

Regardless of cohort, subjects should take ZN-c5 once daily at approximately 24-hour intervals (alternatively, this total daily dose may be divided by 2 and administered BID [every 12 hours]).

In the Phase 1 parts of the study, subjects should take ZN-c5 at least 1 hour before or 2 hours after a meal.

In the Phase 2 parts of the study, ZN-c5 can be taken with or without food.

If the subject vomits or misses a dose, an additional dose should not be taken. The subject should wait and take the next dose at the regularly scheduled time. Subjects should not take more than 1 dose of ZN-c5 at a time. Capsules should be swallowed whole (do not chew, crush, or open them prior to swallowing). Capsules should not be ingested if they are broken, cracked, or otherwise not intact.

6.1.2.2 DOSING AND ADMINISTRATION OF PALBOCICLIB

Palbociclib (IBRANCE®, Pfizer Inc.) at a dose of 125 mg should be taken orally once daily for 21 consecutive days, followed by 7 days off treatment to comprise a complete cycle of 28 days, per the most recent local or US Full Prescribing Information for palbociclib. Subjects should take palbociclib at approximately 24-hour intervals at approximately the same time each day.

On days that PK samples are drawn, palbociclib should be taken with food 2 hours after the ZN-c5 dose.

If a subject vomits or misses a dose, an additional dose should not be taken. The next prescribed dose should be taken at the usual time. Palbociclib should be swallowed whole (do not chew, crush, or open them prior to swallowing). Palbociclib should not be ingested if the medication is broken, cracked, or otherwise not intact.

6.1.3 DEFINITION OF MTD AND RP2D

During both the Monotherapy and Combination Dose Escalation cohorts of the study, dose limiting toxicity (DLT) will be assessed during Cycle 1. A cohort will be expanded from 3 to 6 subjects if one of the initial 3 subjects demonstrates DLT. Cohort expansion or dose escalation will follow the rules outlined in Table 2. Subjects who do not receive at least 24/28 doses of ZN-c5 or at least 18/21 doses of palbociclib in Cycle 1 for reasons other than DLT will be replaced.

Table 2: Dose Escalation Rules

If DLT was observed in:	Then:
0 in 3 subjects	Proceed with enrollment in next cohort
1 of 3 subjects	Enroll 3 additional subjects in current cohort
1 of 6 subjects	Proceed with enrollment in next cohort
≥ 2 subjects in a cohort	Do not escalate; enroll 3 additional subjects in previous
	cohort or new intermediate dose level

The MTD is defined as the highest dose level with ≤ 1 DLT in a cohort of 6 subjects. The RP2D may be lower but will not be higher than the MTD. The MTD/RP2D for monotherapy treatment may be different than the MTD/RP2D for combination therapy.

6.1.4 MONOTHERAPY DOSE ESCALATION

In order to define an MTD or the RP2D for ZN-c5 as a single agent, this study will follow a standard 3+3 design. At least 3 and up to 6 evaluable subjects will be enrolled for each dose cohort. ZN-c5 will be administered orally once daily (alternatively, this total daily dose may be divided by 2 and administered BID [every 12 hours]), on a 28-day cycle (continuous dosing). The total number of patients will depend upon the number of dose escalations necessary, but it is estimated to be approximately 36 subjects.

Dose levels and dosing frequency may be adjusted during the study on the basis of emerging safety and PK data. Intermediate dose levels may be evaluated.

Additional subjects can be enrolled at a lower dose level already deemed well-tolerated; these patients will be part of the Monotherapy Expansion (Section 6.1.6).

At least 6 subjects will be treated at the MTD/RP2D.

The dose levels for the study are shown in Table 3.

Table 3: ZN-c5 Study Dose Levels

Dose Level*	ZN-c5* (once daily)**
1	50 mg
2	75 mg
3	100 mg
4	150 mg
5	300 mg
6	600 mg
7	900 mg
8	1200 mg

^{*}Dose Levels may be modified, and intermittent dose levels may be implemented based on emerging safety and PK results.

6.1.5 COMBINATION DOSE ESCALATION

Dose escalation in combination with palbociclib will be initiated at a ZN-c5 dose that is deemed well-tolerated in the Monotherapy Dose Escalation and will proceed with higher ZN-c5 doses, as tolerated in the Monotherapy Dose Escalation, based on standard rules of 3+3 design in order to define an MTD/RP2D for ZN-c5 in combination with palbociclib (Section 6.1.3). The total number of patients will depend upon the number of dose escalations necessary, but it is estimated to be approximately 40 subjects (including alternate dosing schedules, e.g., BID, and possible backfill).

Dose levels and schedule will follow the dose levels and schedule per the Monotherapy Dose Escalation.

Additional subjects can be enrolled at a lower dose level already deemed tolerated (backfill). At least 6 subjects will be treated at the MTD/RP2D.

The subjects treated in the Combination Dose Escalation can possibly count towards the futility assessment stage accrual (Section 9.2.4, Combination Phase 2).

The dose of palbociclib used in the combination phases of the study will be the Regulatory Authority approved dose and schedule (125 mg PO QD \times 21 days, followed by 7 days off treatment).

6.1.6 MONOTHERAPY EXPANSION

To further assess the safety, tolerability, and preliminary efficacy of ZN-c5, the dose expansion with monotherapy will be initiated at a dose selected based on PK, safety and available biomarker data from the Monotherapy Dose Escalation. Expansion at a specific dose level will continue until a higher dose has been deemed well-tolerated (no DLTs in 3 subjects or at most 1 DLT in 6 subjects), at which point expansion accrual will shift to the higher dose level.

Efficacy in the Monotherapy Expansion will be determined by CBR.

The Monotherapy Expansion overall will target balanced accrual between the 3 lines of therapy (1st, 2nd and 3rd hormonal therapy line) across all dose levels.

^{**} Alternatively, this total daily dose may be divided by 2 and administered BID (every 12 hours).

The total cohort size necessary for futility has been estimated based on futility screening criteria targeting at least 10 evaluable subjects for each line cohort across all dose levels where anti-tumor activity is demonstrated and providing an acceptable false negative risk of concluding that there is no activity if the true CBR is at least 40%. The total number subjects will depend upon the number of dose escalations, but it is not estimated to exceed approximately 45 subjects.

Futility screening

Patients are evaluable for assessment of anti-tumor efficacy (based on CBR) if they were dosed and had at least 1 post-baseline disease/tumor assessment (Section 9.3). CBR as measured using RECIST v.1.1 will be assessed to provide a preliminary, anti-tumor activity evaluation.

6.1.7 MONOTHERAPY PHASE 2

To establish the appropriate dose for further development of ZN-c5, additional subjects will be enrolled to further assess the safety, tolerability, and preliminary efficacy of up to 3 dose levels of single agent ZN-c5 (which can include QD or BID dosing). The ZN-c5 dose levels will be selected based on available safety, PK, anti-tumor activity and biomarker data.

Up to 75 subjects will be enrolled per dose level using a randomized (if 2 or more doses), parallel cohort, non-comparative (estimation) design. Efficacy in the Monotherapy Phase 2 will be determined by CBR and results will be combined with those from subjects with similar treatment characteristics (2nd/3rd Line therapy) and treated at the same dose level of ZN-c5 in the Monotherapy Expansion arm (Section 9.2.3). Therefore, the targeted total N (Phase 2 and same population/dose subjects in the Monotherapy Expansion combined) is 75 subjects per dose level to estimate the CBR rate with certain confidence before proceeding with a larger confirmatory study.

6.1.8 COMBINATION PHASE 2

Following the determination of the MTD/RP2D for ZN-c5 in combination with palbociclib, additional subjects will be enrolled to further assess the safety, tolerability, and preliminary efficacy of ZN-c5 in combination with palbociclib.

ZN-c5 will be administered at the combination RP2D and potentially at a lower dose in combination with palbociclib. The lower ZN-c5 dose will be selected based on available safety, PK and biomarker data.

Efficacy in the Combination Phase 2 will be determined by CBR. The Combination Phase 2 will target balanced accrual between the 2 lines of therapy (1st and 2nd hormonal therapy line) across dose levels.

The Combination Phase 2 portion will follow a randomized, parallel group, non-comparative design, assuming both the RP2D and the lower dose are investigated, or a single dose cohort, if only the RP2D is investigated. Each dose cohort will follow a Simon 2-stage design.

Approximately 56 subjects will be enrolled in each dose cohort. Subjects treated in the Combination Dose Escalation at a demonstrated well-tolerated lower combination dose (no DLTs in 3 subjects or at most 1 DLT in 6 subjects) may also count towards the futility stage accrual, assuming the subjects are evaluable (dosed subjects with at least 1 post baseline disease/tumor assessment [Section 9.3]). The two dose cohorts evaluated in Phase 2 will not use the same subjects from lower dose cohorts in the Phase 1

Combination Dose Escalation phase; for example ZN-c5 50 mg Combination Dose Escalation subjects may count for the 100 mg futility cohort in Phase 2, if that is selected as the lower dose cohort for the Phase 2 component, but will not also count for the RP2D futility cohort, if a higher dose is selected as the RP2D.

Futility (Stage 1) and Efficacy (Stage 2)

Within each dose cohort, 51 evaluable subjects will be enrolled in 2 stages, with 19 subjects in the Futility Stage (Stage 1) and 32 subjects in the Efficacy Stage (Stage 2).

Second stage accrual at each cohort will be completed, assuming that Stage 1 futility criteria are exceeded, with at least 11 subjects with CBR in the first 19 evaluable subjects. An approximate 10% loss for CBR evaluability has been assumed resulting in a total sample size for each dose cohort of approximately 56 subjects or a total sample size of 112 subjects for the Combination Phase 2.

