Efficacy in the Monotherapy Phase 2 will be assessed as in the Monotherapy Expansion and CBR outcomes in the Monotherapy Phase 2 will be combined with those from subjects in the Monotherapy Expansion arm who were treated with ZN-c5 as $2^{nd}/3^{rd}$ Line of treatment and dosed at the same ZN-c5 dose in the Monotherapy Expansion. The sample size is determined in order to estimate the CBR at each dose level with certain confidence before proceeding with a larger confirmatory study. Based on the targeted sample size, the precision for a 95% exact confidence interval around a hypothesized 40-50% CBR rate is \pm 12% at each dose level studied.

Historical estimates for the CBR rate specific to $2^{nd}/3^{rd}$ Line patients (either post CDK4/6 inhibitor or not) are not readily available. The CBR range was estimated based on two studies, reporting a CBR rate for fulvestrant alone of 40% in 2^{nd} Line or higher (PALOMA-3) and 56% CBR in 1^{st} or 2^{nd} Line (MONARCH-2). The targeted precision will be adequately achieved within the specified range and it will increase further outside of the range, if the true CBR rate is further (higher or lower) from 50%.

9.2.4 COMBINATION PHASE 2

The Combination Phase 2 portion follows a randomized, parallel group, non-comparative design, assuming both the RP2D and the lower dose are investigated, or a single dose cohort, if only the RP2D is investigated. Each dose cohort is independently powered (non-comparative) and follows a Simon 2-stage design.

Approximately 56 subjects will be enrolled in each dose cohort. Subjects treated in the Combination Dose Escalation at lower doses can possibly also count towards the futility stage accrual, assuming the subjects are evaluable. The two dose cohorts evaluated in Phase 2 will not use the same subjects from lower dose cohorts in the Phase 1 Combination Dose Escalation phase; for example, ZN-c5 50 mg Combination Dose Escalation subjects may count for the 100 mg futility cohort in Phase 2, if that is selected as the lower dose cohort for the Phase 2 component but will not also count for the RP2D futility cohort, if a higher dose is selected as the RP2D.

CBR as measured using RECIST v.1.1 will be assessed to provide preliminary anti-tumor activity evaluation in a patient population thought most likely to respond to ZN-c5. Subjects are evaluable for CBR if they have at least 1 post baseline disease/tumor assessment (Section 9.3).

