Sample size for each dose cohort is based on a Simon 2-stage design with 80% power at the 1-sided 2.5% alpha level to differentiate between 50% CBR (poor performance) and 70% CBR (promising performance). Fifty-one (51) evaluable subjects will be enrolled in two stages, with 19 subjects in Stage 1 and 32 subjects in Stage 2. The probability of early stopping is 68%. The Combination Phase 2 will target balanced accrual between the 2 lines of prior hormonal therapy (1st and 2nd hormonal therapy line) across dose levels.

Second stage accrual will be completed, assuming that Stage 1 futility criteria are exceeded with at least 11 subjects with CBR in the first 19 evaluable subjects. An approximate 10% loss for CBR evaluability has been assumed resulting in a sample size of approximately 56 subjects for each cohort, resulting in a total sample size of approximately 112 subjects for this trial stage.

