Efficacy in the Monotherapy Phase 2 will be assessed as in the Monotherapy Expansion and CBR outcomes in the Monotherapy Phase 2 will be combined with those from subjects in the Monotherapy Expansion arm who were treated with ZN-c5 as 2nd/3rd Line of treatment and dosed at the same ZN-c5 dose in the Monotherapy Expansion. The sample size is determined in order to estimate the CBR at each dose level with certain confidence before proceeding with a larger confirmatory study. Based on the targeted sample size, the precision for a 95% exact confidence interval around a hypothesized 40 – 50% CBR rate is $\pm 12\%$ at each dose level studied.

Historical estimates for the CBR rate specific to 2nd/3rd Line subjects (either post CDK4/6 inhibitor or not) are not readily available. The CBR range was estimated based on two studies, reporting a CBR rate for fulvestrant alone of 40% in 2nd Line or higher (PALOMA-3) and 56% CBR in 1st or 2nd Line (MONARCH-2). The targeted precision will be adequately achieved within the specified range and it will increase further outside of the range, if the true CBR rate is further (higher or lower) from 50%.

3.5.4 Combination Phase 2

The Combination Phase 2 portion follows a randomized, parallel group, non-comparative design, assuming both the RP2D and the lower dose are investigated, or a single dose cohort, if only the RP2D is investigated. Each dose cohort is independently powered (non-comparative) and follows a Simon 2-stage design.

Approximately 56 subjects will be enrolled in each dose cohort. Subjects treated in the Combination Dose Escalation at lower doses can possibly also count towards the futility stage accrual, assuming the subjects are evaluable. The two dose cohorts evaluated in Phase 2 will not use the same subjects from lower dose cohorts in the Phase 1 Combination Dose Escalation phase; for example, ZN-c5 50 mg Combination Dose Escalation subjects may count for the 100 mg futility cohort in Phase 2, if that is selected as the lower dose cohort for the Phase 2 component but will not also count for the RP2D futility cohort, if a higher dose is selected as the RP2D.

CBR as measured using RECIST v.1.1 will be assessed to provide preliminary anti-tumor activity evaluation in a subject population thought most likely to respond to ZN-c5. Subjects are evaluable for CBR if they have at least 1 post baseline disease/tumor assessment (protocol section 9.3).

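### Stage 1 of a Combination Phase 2 Simon cohort may, at discretion, count escalation subjects treated at a lower ZN-c5 dose, but the stated operating characteristics make no allowance for it

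*Protocol*

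**What the plan says.** Each Combination Phase 2 dose cohort follows a Simon two-stage design with 51 evaluable subjects, 19 in Stage 1 and 32 in Stage 2. Stage 2 accrual requires "at least 11 subjects with CBR in the first 19 evaluable subjects" (protocol 6.1.8 and 9.2.4; SAP 3.4 Table 1 gives the same rule as stopping at 10 or fewer). Protocol 9.2.4 and SAP 3.5.4 state 80% power, 1-sided 2.5% alpha, a 50% versus 70% CBR and 68% early stopping, with no reference to borrowing. They add: "Each dose cohort is independently powered (non-comparative) and follows a Simon 2-stage design".

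Protocol 6.1.8 says that escalation subjects at a well-tolerated lower combination dose "may also count towards the futility stage accrual, assuming the subjects are evaluable", and gives the example "ZN-c5 50 mg Combination Dose Escalation subjects may count for the 100 mg futility cohort in Phase 2". SAP 3.5.4 repeats the permission: "Subjects treated in the Combination Dose Escalation at lower doses can possibly also count towards the futility stage accrual". The conditions are that the lower dose was well tolerated (6.1.8 only), that the subject is evaluable, and that the same subjects are not used for both cohorts. The wording is permissive throughout (may, can possibly, might). Nothing sets how many subjects count, which ones, or when that is decided.

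The two groups enter under different criteria (protocol 5.1). Escalation subjects need ER above 1%, Phase 2 subjects above 10%. HER2 status may come from the medical record in escalation but not in Combination Phase 2. Combination Phase 2 allows at most 1 prior endocrine line for advanced disease; escalation has no such cap. Escalation subjects must be refractory to or intolerant of established therapy, which is not asked of Phase 2 subjects. Criteria 9 (prior endocrine response) and 10c (chemotherapy) are the same.

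**The concern.** A Simon design's stopping probability and power are computed for a single response rate that applies to every subject. Here some of the 19 Stage 1 subjects may have received a lower dose than the one being judged, and may come from a population selected differently. If their CBR is lower than the cohort's, an active dose is stopped too often; if it is higher, an inactive dose continues too often. Because the study is open-label and counting is discretionary, nothing in the text prevents the choice of whom to count from being made after outcomes are known. What is at stake is the go/stop decision for a dose cohort.

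**Working it through.** **Inputs from the documents.** n1 = 19, n2 = 32, n = 51; continue if at least 11 of 19; CBR 50% (poor) and 70% (promising); 80% power; 1-sided alpha 2.5%; early stopping 68%.

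**Inputs not in the documents (assumed).** The number borrowed, k = 3 or 6, is taken from the two well-tolerated cohort sizes named in protocol 6.1.8. The CBR of borrowed subjects, q, is varied. The final success boundary is inferred below.

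**Step 1: reproduce the plan.** With X1 ~ Bin(19, p):
- Early stopping at p = 0.50: P(X1 ≤ 10) = 0.6762, the stated 68%.
- Wrongful stopping at p = 0.70: P(X1 ≤ 10) = 0.0839.

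Success requires X1 ≥ 11 and X1 + Bin(32, p) ≥ c:

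| c (of 51) | alpha at 0.50 | power at 0.70 |
|---|---|---|
| 32 | 0.0392 | 0.8513 |
| 33 | 0.0219 | 0.8014 |
| 34 | 0.0112 | 0.7294 |

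Of these, only c = 33 meets both stated limits, so 33/51 is used from here on. The plan's figures are correct for a cohort without borrowing.

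**Step 2: add k borrowed subjects with CBR q.** The gate becomes A + Bin(k, q) ≥ 11, where A ~ Bin(19 − k, p) counts the cohort's own Stage 1 subjects.
- *Gate-only:* borrowed subjects serve the futility look but not the final count. Success needs the gate and A + B ≥ 33, with B ~ Bin(32 + k, p), so that the final 51 are all Phase 2 subjects.
- *Enter:* borrowed subjects stay in the 51. Success needs the gate and A + Bin(k, q) + Bin(32, p) ≥ 33.

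Results for true cohort CBR p = 0.70:

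| k | q | P(wrongful stop) | power, gate-only | power, enter |
|---|---|---|---|---|
| 0 | – | 8.4% | 80.1% | 80.1% |
| 3 | 0.65 | 9.7% | 78.6% | 78.5% |
| 3 | 0.60 | 11.0% | 77.7% | 76.7% |
| 3 | 0.50 | 13.9% | 75.8% | 73.1% |
| 6 | 0.70 | 8.4% | 78.8% | 80.1% |
| 6 | 0.65 | 11.0% | 76.9% | 76.7% |
| 6 | 0.60 | 14.1% | 74.7% | 73.0% |
| 6 | 0.50 | 21.6% | 69.2% | 64.7% |

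The row with q = 0.70 shows that equal CBR is enough to preserve the stopping probability. The stated power also needs the borrowed subjects to be in the final 51.

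**Step 3: true cohort CBR p = 0.50, k = 6.** Early stopping moves from 67.6% to 77.0% if q = 0.40, or to 57.1% if q = 0.60. The error can therefore go either way.

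**Step 4: alpha.** Under gate-only, success always requires at least 33 of 51 Phase 2 subjects, so alpha cannot exceed P(Bin(51, 0.5) ≥ 33) = 2.44%, whatever the borrowed subjects do. Under enter, 6 borrowed at q = 0.60 in a 50% cohort would give 3.3%.

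**Step 5: which reading?** The counting permission extends only to futility-stage accrual. SAP 6.1 summarises endpoints by study part and by the dose received on the first day of treatment, so a lower-dose escalation subject would not appear in the higher-dose Phase 2 CBR. Both points favour gate-only. Because 51 is built as 19 + 32, some ambiguity remains.

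**The case against.** The strongest reply is that this is a disclosed design choice with stated conditions, that the published figures are right for the design as specified, and that every Simon calculation assumes homogeneity. The documents also show no CBR gap between adjacent well-tolerated doses, and at a 5-point gap the loss is 1 to 3 points. The criteria are called guiding (protocol 9.4.7, SAP 3.4), whereas the calculation treats them as binding. All analyses are descriptive (protocol 9.1, SAP 3.3). SAP 5.2 and 7 make Combination Phase 2 conditional, and the SAP (17 Feb 2023) postdates the 18 May 2022 data cut-off. SAP 6.6.3 specifies separate per-drug adverse-event summaries only for the Phase 1 Combination, which hints that the Phase 2 part was not run but does not prove it.

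Much of this stands and limits the weight of the point. It does not remove it: the rule as written can still decide a dose on subjects who never received it, with their number and selection left open.

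A reader might infer four stronger things that the documents do not support:
- **Inflated type I error.** Gate-only counting, the better-supported reading, caps alpha at 2.44%, and no formal test is planned.
- **A false claim of independent powering.** The phrase is qualified as non-comparative, so it says that each cohort is sized on its own. It does not promise a homogeneous Stage 1.
- **Borrowing of most of the roughly 40 escalation subjects.** Stage 1 has only 19 places, and only subjects at well-tolerated lower doses qualify.
- **A breach of the protocol's own pooling standard.** The same-dose pooling in protocol 6.1.7 concerned the final monotherapy CBR estimate, not a futility look, and SAP 8 replaced it with analysis by phase.

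**Conclusion.** The concern holds in this form: lower-dose escalation subjects, enrolled under different criteria, may be counted at discretion in a higher-dose cohort's 11-of-19 decision, with no number or outcome-blind selection rule, and the stated operating characteristics do not say that they exclude this. On the gate-only reading with 6 borrowed, the loss runs from about 3 power points (assumed CBR 65%) to about 11 (50%), with wrongful stopping of 11 to 22% against 8.4%. With 3 borrowed at 65% it is under 2 power points. The sizes rest on assumed values of k and q, an inferred 33/51 boundary and a gate treated as binding. The consequence is a wrong go/stop decision, not a confirmatory error, and it arises only if Combination Phase 2 is run; the SAP does not say whether it was. The plan should be changed, but the point is not critical.

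**What to change.** In protocol 6.1.8 and 9.2.4 (aligning 6.1.5 and 9.2.1) and SAP 3.5.4, state that a Combination Dose Escalation subject counts toward Stage 1 of a dose cohort only if treated at that cohort's own ZN-c5 dose level and meeting the Combination Phase 2 eligibility criteria; that all such evaluable subjects count, regardless of outcome; and whether they enter the final 51.

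If lower-dose counting is kept, fix the number and the selection rule without regard to outcome, state that the 80%, 2.5% and 68% figures assume no such borrowing, and give the operating characteristics over a range of borrowed-subject CBRs.

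If Stage 1 has already accrued, list the counted subjects by dose and report the Stage 1 count with and without them. This needs only existing data and is the useful part if the wording can no longer affect accrual.

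The cost is somewhat slower Stage 1 accrual: each lower-dose subject no longer counted needs one more Phase 2 subject before the futility look. The stated 56 per cohort and 112 in total do not change. Same-dose counting remains possible at the RP2D, where protocol 6.1.5 plans at least 6 escalation subjects at the MTD/RP2D, provided that they meet Phase 2 eligibility. If Combination Phase 2 is not run, the change has neither cost nor effect.
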